6.6.7.2 Columbia-Suicide Severity Rating Scale

The C-SSRS is a clinician-rated instrument that reports the severity of both suicidal ideation and behavior. Suicidal ideation is classified on a 5-item scale: 1 (wish to be dead), 2 (nonspecific active suicidal thoughts), 3 (active suicidal ideation with any methods [not plan] without intent to act), 4 (active suicidal ideation with some intent to act, without specific plan), and 5 (active suicidal ideation with specific plan and intent). The C-SSRS also captures information about the intensity of ideation, specifically the frequency, duration, controllability, deterrents, and reasons for the most severe types of ideation. Suicidal behavior is classified on a 5-item scale: 0 (no suicidal behavior), 1 (preparatory acts or behavior), 2 (aborted attempt), 3 (interrupted attempt), and 4 (actual attempt). More than 1 classification can be selected provided they represent separate episodes. For actual attempts only, the actual or potential lethality is classified for the initial, most lethal, and most recent attempts. The C-SSRS will be completed at all study visits. At Visit 1 (Screening), the C-SSRS will be completed for the patient's lifetime history of suicidal ideation and behavior. At all other visits the C-SSRS will be completed for ideation and behavior since the previous visit.

The C-SSRS will be completed by a trained rater with extensive professional training.

6.7 Summary of Methods of Data Collection

An IWRS will be used to dispense IP, randomize patients, and manage IP inventory. All other data for this study will be collected using eCRFs via an electronic data capture system, except for ECG and laboratory data.

A qualified central ECG reader will be used for the analysis of all ECGs and central laboratory for blood and urine samples. ECG and laboratory data will be transferred to AbbVie or its designee on a periodic basis throughout the study.

7. Statistical Procedures

7.1 Analysis Populations

Seven populations will be considered in the statistical analysis of this study.

7.1.1 Screened Population

The screened population will consist of all patients who underwent a Screening Visit and received a PID number.

7.1.2 Open-label Safety Population

The OL safety population will consist of all patients in the screened population who took at least 1 dose of open-label cariprazine during the OL period of the study.

7.1.3 Open-label Intent-to-Treat Population

The OL intent-to-treat (ITT) population will consist of all patients in the OL safety population who had at least 1 postbaseline assessment of the YMRS, MADRS, or CGI-S scores during the OL period of the study.

7.1.4 Open-label Safety-Follow-up Population

The open-label safety-follow-up (OL SFU) population will consist of patients in the OL safety population who were not randomized.

7.1.5 Randomized Population

The randomized population will consist of all patients in the OL safety population who were randomized to a treatment group during the DB treatment period of the study.

7.1.6 Double-blind Safety Population

The DB safety population will consist of all patients in the randomized population who took at least 1 dose of DB IP.

7.1.7 Double-blind Intent-to-Treat Population

The DB ITT population will consist of all patients in the DB safety population who had at least 1 post-randomization assessment of the YMRS, MADRS, or CGI-S scores during the DB period of the study.

7.2 Collection and Derivation of Primary and Secondary Efficacy Assessments

7.2.1 Primary Efficacy Variable

The primary efficacy parameter is the time to first relapse of any mood episode during the DB period. The time to first relapse is defined as the number of days from randomization to the first relapse.

Relapse criteria include any of the following:

- YMRS total score ≥ 17
- MADRS total score ≥ 20
- CGI-S > 4
- Initiation of treatment with a mood stabilizer, antidepressant, antipsychotic agent, or with a benzodiazepine that exceeds the protocol-specified allowance or duration (ie, more than 2 mg/d of lorazepam equivalent or for more than 3 consecutive days) to treat worsening mood symptoms as judged by the clinical impression of the investigator,
- Psychiatric hospitalization
- Exacerbation of illness as judged by clinical impression of investigator (eg, clinically significant agitation, suicidal or homicidal ideations)

For patients who meet relapse criteria, the investigator will categorize the relapse event(s) as manic or depressive event(s), with or without mixed features.

7.2.2 Secondary Efficacy Variable

None.

7.2.3 Other Efficacy Variables

Additional efficacy parameters include:

- Change from baseline in YMRS total score by visit during OL and DB period
- Change from baseline in MADRS total score by visit during OL and DB period
- Change from baseline in CGI-S score by visit during OL and DB period
- CGI-I score by visit during OL and DB period
- Change from baseline in PSP score by visit during OL and DB period

Additional efficacy parameters only for the DB treatment period include:

- Time to manic episode
- Time to depressive episode

Manic episode with mixed features or depressive episode with mixed features are classified as manic or depressive episodes, respectively.

7.3 Hypothesis and Methods of Analysis

All efficacy analyses for the OL will be performed using the OL ITT population, unless stated otherwise. Baselines for efficacy parameters in the OL period will be defined as the last non-missing efficacy assessment before the first dose of OL IP. All efficacy analyses for the DB period will be performed using the DB ITT population, unless stated otherwise. Baselines for the additional efficacy parameters in the DB period will be defined as the last nonmissing efficacy assessment before the first dose of DB IP. All statistical tests will be 2-sided hypothesis tests performed at the 5% level of significance and all confidence intervals will be 2-sided 95% confidence intervals, unless stated otherwise.

7.3.1 Primary Efficacy Analyses

The primary efficacy analysis is to evaluate the time to first relapse of any mood episode in bipolar I disorder patients who responded to OL treatment with cariprazine.

The primary null hypothesis is that the distribution of the time to first relapse for each of the cariprazine 3.0 mg/d and 1.5 mg/d treatment groups is not different from that for the placebo treatment group. The alternative primary hypothesis is that the distribution of the time to first relapse for each of the cariprazine 3.0 mg/d and 1.5 mg/d treatment group is different from that for the placebo treatment group.

The hypothesis testing will compare the time to relapse between each cariprazine group and placebo group using the log-rank test stratified by modified index episode (manic or depressive) for the DB ITT population. To derive the modified index episode, the manic index episode(s) with or without mixed features will be classified as manic episode(s); depressive index episode(s) with or without mixed features will be classified as depressive episode(s). Estimates of the hazard ratio (HR) and 95% confidence intervals will be based on the Cox proportional hazards model with treatment group as covariates stratified by modified index episode (manic or depressive). The Kaplan-Meier estimates for the cumulative distribution of the relapse rate for each treatment group will be provided.

The primary hypotheses for cariprazine 3.0 mg/d and 1.5 mg/d treatment groups versus placebo will be tested sequentially in order to control the overall Type I error rate. The comparison of cariprazine 3.0 mg/d versus placebo will be tested first at the two-sided 0.05 significance level, only when it is significant, the comparison of cariprazine 1.5 mg/d versus placebo will be tested also at the two-sided 0.05 significance level. This testing strategy controls the overall Type I error rate at the 0.05 significance level.

Two sensitivity analyses will be performed to assess the robustness of the primary analysis results to the possible violation of the noninformative censoring assumption. The first sensitivity analysis will be based on the delta-adjusted method examined by Zhao et al. (2014), which specifies that the hazard of having an event for subjects who discontinued before the time point is increased relative to the hazard for subjects who continued beyond the time point for the experimental treatment group. The delta-adjustment will be gradually increased from zero until reaching the tipping point when the statistical significance of the primary efficacy endpoint is overturned, and the plausibility of the magnitude of delta-adjustment needed for reaching the tipping point will be subject to clinical scrutiny.

The second sensitivity analysis is an extension of the placebo-based pattern mixture model (Lu 2014; Lu 2015). The placebo-based pattern mixture model assumes that patients who discontinued from the cariprazine treatment groups would have disease progression after discontinuation similar to that of placebo. The extended placebo-based pattern mixture model uses a sensitivity parameter to characterize the gradual deviation from the noninformative censoring underlying the primary analysis toward the informative censoring underlying the placebo-based pattern mixture model. The extended placebo-based pattern mixture model sensitivity analysis for time-to-event data is described as follows:

Let $h_0(t)$ denote the baseline hazard function associated with the placebo group. Let β_1 and β_2 denote the treatment effects in terms of log HRs under noninformative censoring for cariprazine 1.5 mg/d versus placebo and cariprazine 3.0 mg/d versus placebo, respectively. The hazard functions associated with the cariprazine 1.5 and 3.0 mg/d groups under noninformative censoring are thus given by $h_1(t) = h_0(t) \exp(\beta_1)$ and $h_2(t) = h_0(t) \exp(\beta_2)$, respectively. Consider the extended placebo-based pattern mixture model sensitivity analysis. For the placebo group, we assume that patients with premature discontinuation would have comparable experience after discontinuation to their counterparts without premature discontinuation. For the cariprazine treatment groups, each dropout time point for cariprazine patients defines a missing data pattern, and we assume that patients with premature discontinuation would have disease progression after discontinuation somewhere between their counterparts without premature discontinuation and patients in the placebo group. Specifically, we assume that $h_1(t) = h_0(t) \exp((1 - \phi)\beta_1)$ and $h_2(t) =$

 $h_0(t) \exp((1-\phi)\beta_2)$ for t > C, where C denotes the time of premature discontinuation. The sensitivity parameter $\phi \in [0,1]$ characterizes the gradual deviation from the noninformative censoring with $\phi = 0$ toward the informative censoring underlying the placebo-based pattern mixture model with $\phi = 1$. A multiple imputation approach will be used to implement the extended placebo-based pattern mixture model.

7.3.2 Secondary Efficacy Analyses

None.

7.3.3 Other Efficacy Analyses

The overall relapse rate, as well as the relapse rates for sub-categories of interest including manic episode and depressive episode will be presented.

Time to early discontinuation for any reason during the DB treatment period for the ITT population will be analyzed.

These efficacy parameters will be analyzed using the same method used to analyze the primary efficacy variable.

The following continuous efficacy variables will be summarized by visit for the OL and DB treatment periods separately for the corresponding ITT populations. For the DB treatment period, the variables for YMRS, MADRS, CGI-S, and CGI-I will be analyzed by using a mixed-effects model for repeated measures (MMRM) with treatment group, region (US and non-US), modified index episode strata (manic or depressive), visit, and treatment group-by-visit interaction as fixed effects and the baseline value and baseline-by-visit interaction as the covariates. An unstructured covariance matrix will be used. The Kenward-Roger approximation will be used to estimate denominator degrees of freedom.

Descriptive statistics will be provided at each assessment time point by treatment group for the change from baseline in PSP score.

For Open-label Treatment Period

- Change from baseline in YMRS total score by visit
- Change from baseline in MADRS total scores by visit
- Change from baseline in CGI-S score by visit
- CGI-I score by visit
- Change from baseline in PSP score by visit

For Double-blind Treatment Period

- Change from DB baseline in YMRS total score by visit
- Change from DB baseline in MADRS total score by visit
- Change from DB baseline in CGI-S score by visit
- CGI-I score by visit
- Change from DB baseline in PSP score by visit

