8.4.6 Final or Early Termination Visit (Visit 31)

The following procedures will be carried out at the Final Visit at the end of the DB treatment period (Visit 31) or at ET:

- Collect blood sample for serum pregnancy test (women of child-bearing potential only)
- Collect blood samples for clinical laboratory determinations
- Collect blood sample for Hemoglobin A1c
- Review concomitant medications
- Assess YMRS, MADRS, CGI-S, CGI-I, PSP, C-SSRS
- Assess patient for relapse (per Section 4.7)
- Have patient complete the WPAI-BD QoL questionnaire
- Evaluate EPS symptoms (AIMS/BARS/SAS)
- Collect vital signs measurements, including weight and waist circumference
- Perform physical examination
- Perform ECG

- Review and assess AEs and SAEs
- Collect blood for PK evaluation
- Collect IP blister card(s) and perform drug compliance and accountability

8.4.7 Safety Follow-up Visits 32 and 33

Patients who complete the study, and those who prematurely discontinue from either the OL or DB treatment periods, will enter a 4-week SFU period (2 visits, 1 at the end of every 2 weeks). During the SFU period, patients will be stabilized on appropriate medications, and additional evaluations (laboratory studies, ECG, etc) may be performed as deemed necessary by the investigator. This period may also be used for follow-up and management of all abnormal findings and AEs observed during OL or DB treatment periods. No IP will be administered during the SFU period.

- Collect blood sample for serum pregnancy test (women of child-bearing potential only [Visit 33 only])
- Review concomitant medications
- Collect vital signs measurements (including weight)

Review and assess AEs and SAEs

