8.8 Early Discontinuation of Patients

Patients may discontinue from the study at any time for any reason. Discontinuation is permanent; once a patient is discontinued, he/she shall not be allowed to enroll again.

Patients can be prematurely discontinued from the study for one of the following reasons:

- AE
- Noncompliance with protocol
- Noncompliance with IP dosing regimen
- Withdrawal of consent (a clear reason must be documented when possible)
- Lost to follow-up (every effort must be made to contact the patient; a certified/traceable letter must be sent)
- Study terminated by sponsor
- Site terminated by sponsor
- Pregnancy
- Other reasons

Notification of early patient discontinuation from the study and the reason for discontinuation will be clearly documented on the appropriate eCRF page. Patients who take IP during the study (OL treatment period or the DB treatment period) and who prematurely discontinue from the study, regardless of cause, should be seen for a final assessment. A final assessment will be defined as completion of the evaluations scheduled for Visit 31/ET. If the patient discontinues after IP is taken, the patient is also expected to return for 2 safety follow-up visits, Visit 32 (2 weeks after completion of the ET visit) and Visit 33 (4 weeks after completion of the ET visit).

At a minimum, collect the following information when a patient discontinues:

- 1. The reason the patient discontinued;
- 2. The date of the last dose of test products from the trial;
- 3. The date of the last assessment and/or contact. A follow-up contact (telephone or visit) will be arranged as appropriate;
- 4. (S)AEs;
- 5. Compliance with the test product administration as specified in this protocol;
- 6. Final Assessments: Unless there is withdrawal of consent, every effort should be made to ensure that all procedures and evaluations scheduled for Visit 31/ET and subsequently Visits 32 and 33 (SFU Period) are performed (Table 1, Schedule of Visits and Procedures).
- 7. Retrieve all IP(s) from the patient.

For all patients who discontinue as a result of being lost to follow-up, a determination must be noted in the eCRF as to whether the loss is related to an acute exacerbation of bipolar disorder.

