6.7 DOUBLE-BLIND INTENT-TO-TREAT POPULATION

The DB ITT Population will consist of all who took at least 1 dose of DB IP and had at least 1 post-randomization assessment of the YMRS, MADRS, or CGI-S scores during the DBTP of the study, or had a relapse event.

Patients will be included in the randomized treatment group for the DB ITT population.

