10.3 ADDITIONAL EFFICACY PARAMETERS

The overall relapse rate, as well as the relapse rates for sub-categories of interest including modified manic episode and modified depressive episode will be presented.

Time to early discontinuation with any reason (including relapse) during the DBTP for the DB ITT population will be analyzed using the same method used to analyze the primary efficacy variable.

For the following continuous efficacy variables, the change from baseline refers to the change from OL baseline during the OLTP, and the change from DB baseline during the DBTP, unless stated otherwise.

For Open-label Treatment Period

- Change from baseline in YMRS total score by visit
- Change from baseline in MADRS total scores by visit
- Change from baseline in CGI-S score by visit
- CGI-I score by visit
- Change from baseline in PSP total score and sub-domain score by visit

For Double-blind Treatment Period

- Change from DB baseline in YMRS total score by visit
- Change from DB baseline in MADRS total score by visit
- Change from DB baseline in CGI-S score by visit
- CGI-I score by visit
- Change from DB baseline in PSP total score and sub-domain score by visit

Descriptive statistics (n, mean, standard deviation, median, Q1, Q3, minimum and maximum) for additional efficacy parameters will be provided by visit for the OL ITT population and the DB ITT population using both last-observation-carried forward (LOCF) and observed cased (OC) approaches. LOCF approach will be used to impute missing postbaseline values. Imputation of missing values will be done for the OLTP and the DBTP separately.

For the DBTP, the additional efficacy parameters will be analyzed by using a mixed-effects model for repeated measures (MMRM) with treatment group, region (US and non-US), modified index episode strata (manic or depressive), visit, and treatment group-by-visit interaction as fixed effects and the baseline value and baseline-by-visit interaction as the covariates. An unstructured covariance matrix will be used. The Kenward-Roger approximation ([Kenward and Roger, 1997](#)) will be used to estimate denominator degrees of freedom. The analysis will be performed based on post-DB baseline scores using only the OC without imputation of missing values. Least squares mean and their standard errors based on the MMRM analysis will be plotted by treatment group and visit.

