17.2 SAFETY AND OTHER EVALUATIONS

This section specifies analyses related to COVID-19 pandemic from the following aspects:

- Disposition
- Study visit (missing entire visit due to COVID-19 or missing assessments due to COVID-19)
- Protocol deviation
- Study drug disruption due to COVID-19

- TEAEs related with COVID-19 and supplemental signs and symptoms
- COVID-19 status (COVID-19 testing results or contact with a COVID-19 positive person)

OL Safety Population or DB Safety Population will be used for the planned analyses described above. The number of participants impacted by COVID-19 during the OLTP will be summarized overall and the number of participants impacted by COVID-19 during the DBTP will be summarized by treatment group and overall. In addition, the number of patients impacted by COVID-19 and their corresponding disposition status in the OLTP and DBTP will be summarized respectively.

The number of patients who missed at least one entire visit due to COVID-19 will be summarized overall for the OLTP and by treatment group and overall for the DBTP. Furthermore, the number of patients who missed at least one assessment due to COVID-19 will be summarized by assessment category (laboratory, C-SSRS, urine pregnancy test, vital signs, ECG, and ophthalmological assessments) and overall. Similar summaries will be provided by visit.

The number of patients with significant protocol deviation due to COVID-19 will be provided. The number of patients with study drug disruption due to COVID-19 will be provided as well. The number of participants with TEAEs related to coronavirus infection or coronavirus test positive will be provided. Supporting listings for the described analyses above will also be provided.

18.0**CHANGES TO ANALYSES SPECIFIED IN PROTOCOL**

1. The definition of the DB ITT population in this document Section 6.7 was updated and overwrites the one specified in the Protocol Amendment 5, and reads as follows:

The DB ITT Population will consist of all who took at least 1 dose of DB IP and had at least 1 post-randomization assessment of the YMRS, MADRS, or CGI-S scores during the DBTP of the study, or had a relapse event.

2. The cutoff for the Age group in the SAP Section 7.4 was updated from 55 to 45 years old, due to imbalance between <55 and >=55 years based on the blinded data review. Now it reads as:

- Age group (< 45 years, \geq 45 years).

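### Time to early discontinuation for any reason is run in the double-blind ITT population, which drops never-dosed patients and unrated non-relapse leavers although their leaving is an event of that analysis

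*Protocol*

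**What the plan says.** Protocol 7.3.3 states: "Time to early discontinuation for any reason during the DB treatment period for the ITT population will be analyzed", with the method of the primary analysis. SAP 10.3 keeps the method and spells out the event and the population: "Time to early discontinuation with any reason (including relapse) during the DBTP for the DB ITT population will be analyzed".

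Protocol 7.1.7 builds the DB ITT population from patients dosed in the double-blind period "who had at least 1 post-randomization assessment of the YMRS, MADRS, or CGI-S scores during the DB period of the study". SAP 6.7 widens this to dosed patients who "had at least 1 post-randomization assessment of the YMRS, MADRS, or CGI-S scores during the DBTP of the study, or had a relapse event". (I read the dose requirement as applying to both branches of that sentence.) SAP 18.0 settles which text applies: "The definition of the DB ITT population in this document Section 6.7 was updated and overwrites the one specified in the Protocol Amendment 5".

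Four other provisions bear on who ends up outside the population:

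- Protocol 8.8: patients who took product and then leave, whatever the cause, "should be seen for a final assessment. A final assessment will be defined as completion of the evaluations scheduled for Visit 31/ET".
- Protocol 8.4.6: the list for that visit contains "Assess YMRS, MADRS, CGI-S, CGI-I, PSP, C-SSRS".
- SAP 7.1: the double-blind period runs from randomization to Visit 31 or early termination, so ratings at the early-termination visit count towards membership.
- Protocol 7.1.5 and SAP 6.5: a Randomized Population is already defined, with no dose or rating condition for the double-blind period.

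**The concern.** The endpoint is leaving the double-blind period. No scale score is needed to know that a patient left. Protocol 8.8 requires the site to record at least the reason, the date of the last dose and the date of the last assessment or contact. Membership of the DB ITT population nevertheless depends on something observed after randomization, which leaving early can itself prevent.

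The relapse clause in SAP 6.7 makes the treatment of unrated patients uneven. SAP Appendix IV explains that Amendment 3 added it so that relapses in patients without efficacy assessments would be counted. Take two dosed, unrated patients who leave on the same day. The one who relapsed is in the analysis. The one who left for an adverse event, withdrew consent or was lost to follow-up is not. Both are events under SAP 10.3.

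The documents show how unrated leavers can arise. Protocol 8.8 makes an exception to the final-assessment effort when consent is withdrawn, and it lists loss to follow-up as a reason for leaving. Protocol 12.13.5 omits efficacy assessments when the early-termination procedures fall more than 2 weeks after the last dose.

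At stake is the early part of the all-cause discontinuation curves, which is estimated without some of the patients who left first.

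**Working it through.** **Inputs.** 126 patients per arm, 39 weeks, relapse hazard ratio 0.42 and 26% discontinuing for other reasons (Protocol 7.5); 35% placebo relapse at Week 39 (SAP 14.0). The first scheduled double-blind rating is Visit 13, 14 days after Visit 12, with a window of ±3 days (Protocol Table 1). Constant hazards and independent dropout are my assumptions. Time is in units of 39 weeks (273 days).

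**Hazards.** Dropout d = −ln(0.74) = 0.301. Relapse l = −ln(0.65) = 0.431 on placebo and 0.42 × 0.431 = 0.181 on each dose.

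**Check against the plan's figure.** Expected relapses per arm = 126 × l/(l+d) × (1 − exp(−(l+d))). This gives 38.5 on placebo and 18.1 on each dose, total 74.7, against the stated 75. The model reproduces the plan. The plan gives no figure for the discontinuation analysis.

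**All-cause events over 39 weeks.** 126 × (1 − exp(−(l+d))) = 65.4 on placebo and 48.2 on each dose, about 162 in total (75 relapses and 87 other).

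**Non-relapse leavers before Visit 13.** 126 × d/(l+d) × (1 − exp(−(l+d) × t/273)):

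| First visit on | Placebo | Each dose | All three arms |
|---|---|---|---|
| Day 11 | 1.51 | 1.51 | 4.5 |
| Day 14 | 1.91 | 1.92 | 5.8 |
| Day 17 | 2.31 | 2.33 | 7.0 |

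At Day 14 this is 5.8/378 = 1.5% of patients and 5.8/162 = 3.6% of the events. It is the number lost if none of these leavers is rated at early termination, so it is an upper figure for dosed patients under a constant hazard.

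**Effect on the curve at Week 2, if none is rated.** All-cause risk is 1 − exp(−(l+d) × 14/273) = 3.68% on placebo and 2.44% on each dose, or 4.64 and 3.08 patients. Removing the leavers from numerator and denominator:

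- placebo (4.64 − 1.91)/(126 − 1.91) = 2.20%
- each dose (3.08 − 1.92)/(126 − 1.92) = 0.93%

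**Effect on the comparison.** The placebo-minus-dose difference goes from 3.68 − 2.44 = 1.24 points to 2.20 − 0.93 = 1.27 points. For the whole period, person-time is 65.4/0.732 = 89.3 on placebo and 48.2/0.482 = 100.0 on each dose. The all-cause hazard ratio goes from 0.482/0.732 = 0.66 to ((48.2 − 1.9)/100.0)/((65.4 − 1.9)/89.3) = 0.65, ignoring the short follow-up of those removed.

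**Front-loaded dropout (assumption; the documents give no pattern).** Non-relapse leavers over 39 weeks number 65.4 − 38.5 = 26.9 on placebo and 48.2 − 18.1 = 30.1 on each dose. If 10% to 20% of them left in the first two weeks and none was rated, 2.7 to 5.4 placebo patients and 3.0 to 6.0 per dose arm would be lost.

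**Never-dosed patients.** These would add to every figure above. The documents give no number for them.

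**The case against.** A reader might infer that the earliest discontinuations are excluded as such, so that the analysis is conditional on reaching the first scheduled visit. The documents do not support that. A leaver is expected at Visit 31/ET, one of three scales is enough for membership, the visit lies inside the double-blind period, and an unrated relapse also qualifies. Leaving before Visit 13 excludes nobody by itself; a dosed patient is out only with no rating at all and no relapse.

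A reader might also infer that an imbalance in very early dropout would be hidden. It would not be. SAP 7.1 reports the Randomized, DB Safety and DB ITT counts by arm. Randomized minus DB Safety gives the never-dosed patients, and DB Safety minus DB ITT gives the dosed, unrated non-relapsers, apart from any patient who received the wrong arm's product. SAP 7.1 also tabulates premature discontinuation by arm and reason in the DB Safety Population. SAP 11.1 summarises adverse events leading to discontinuation by arm. Nothing in the plan makes this efficacy analysis the instrument for detecting early intolerance.

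It is also fair to say that the comparison barely changes, that the analysis lies outside the sequential primary tests, and that the DB ITT population keeps it parallel to the relapse analysis. A patient lost to follow-up also has no exact discontinuation date, so a convention is needed.

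All of this limits the size of the problem and stands. It does not justify the population. Counts and reasons do not repair a time-to-event curve, and the disposition table is a different quantity because SAP 7.1 counts relapsers as completers. Keeping the DB ITT run as supportive preserves the parallel with the primary analysis.

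**Conclusion.** The point holds in a narrow form. The DB ITT population excludes never-dosed patients and dosed patients who leave without relapse and without any rating, and this analysis thereby drops events of its own endpoint. Under a constant 26% dropout hazard with no early-termination ratings, the loss is at most about 1.9 dosed patients per arm, about 6 of 378. Ratings at early termination lower that figure; front-loaded dropout or never-dosed patients raise it. The early part of each curve is slightly understated. Because the modelled loss is nearly equal across arms, the contrast is almost unaffected; an unequal loss is possible, but nothing in the documents indicates one. The primary analysis, the sample size and type I error control are not touched. This is a minor improvement to a non-primary analysis.

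**What to change.** In Protocol 7.3.3 and SAP 10.3, name the Randomized Population, by randomized arm, for time to early discontinuation for any reason. Keep the same stratified log-rank test and Cox model. Use the recorded discontinuation date as the event date, and the last contact date for patients lost to follow-up. The DB ITT version may stay as a supportive run. If the protocol is not amended again, record the change in SAP 18.0.

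The cost is one population flag and one sentence on dates. No new data are needed, since Protocol 8.8 already collects the reason and the dates.
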